2.2 Institutional Review Board/Independent Ethics Committee

Before study initiation, the investigator must have written and dated approval/favorable opinion from the IRB/IEC for the protocol, consent form, subject recruitment materials (eg, advertisements), and any other written information to be provided to subjects. The investigator or BMS should also provide the IRB/IEC with a copy of the IB or product labeling information to be provided to subjects and any updates.

The investigator or BMS should provide the IRB/IEC with reports, updates and other information (eg, expedited safety reports, amendments, and administrative letters) according to regulatory requirements or institution procedures.

2.3 Informed Consent

Investigators must ensure that subjects are clearly and fully informed about the purpose, potential risks, and other critical issues regarding clinical studies in which they volunteer to participate.

In situations where consent cannot be given to subjects, their legally acceptable representatives (as per country guidelines) are clearly and fully informed about the purpose, potential risks, and other critical issues regarding clinical studies in which the subject volunteers to participate.

BMS will provide the investigator with an appropriate (ie, Global or Local) sample informed consent form(s) [ICF(s)] which will include all elements required by ICH, GCP and applicable regulatory requirements. The sample ICF will adhere to the ethical principles that have their origin in the Declaration of Helsinki.

Investigators must:

- Provide a copy of the consent form(s) and written information about the study in the language in which the subject is most proficient prior to clinical study participation. The language must be nontechnical and easily understood.
- Allow time necessary for subject or subject's legally acceptable representative to inquire about the details of the study.
- Obtain an informed consent signed and personally dated by the subject or the subject's legally acceptable representative and by the person who conducted the informed consent discussion.
- Obtain the IRB/IEC's written approval/favorable opinion of the written ICF(s) and any other information to be provided to the subjects, prior to the beginning of the study, and after any revisions are completed for new information.
- If informed consent is initially given by a subject's legally acceptable representative or legal guardian, and the subject subsequently becomes capable of making and communicating his or her informed consent during the study, consent must additionally be obtained from the subject.
- Revise the informed consent whenever important new information becomes available that is relevant to the subject's consent. The investigator, or a person designated by the investigator, should fully inform the subject or the subject's legally acceptable representative or legal guardian, of all pertinent aspects of the study and of any new information relevant to the subject's willingness to continue participation in the study. This communication should be documented.

The confidentiality of records that could identify subjects must be protected, respecting the privacy and confidentiality rules applicable to regulatory requirements, the subjects' signed ICF, and, in the US, the subjects' signed Health Insurance Portability and Accountability Act Authorization.

The consent form(s) must also include a statement that BMS and regulatory authorities have direct access to subject records.

The rights, safety, and well-being of the study subjects are the most important considerations and should prevail over interests of science and society.

3 INVESTIGATIONAL PLAN

3.1 Study Design and Duration

This is a Phase 1/2, open-label study to characterize the safety and tolerability of BMS-986183 administered as a single agent and in combination with nivolumab to subjects with HCC. The study has 4 parts: Part 1 (Phase 1 - BMS-986183 dose escalation), Part 2 (Phase 2 - BMS-986183 dose

expansion), Part 3 (Phase 1 - BMS-986183 and nivolumab dose escalation), and Part 4 (Phase 2 - BMS-986183 and nivolumab dose expansion). BMS-986183 dose escalation (Part 1) and BMS-986183 and nivolumab dose escalation (Part 3) will include subjects with HCC who have received and either progressed or been refractory or intolerant to at least 1 standard prior systemic treatment regimen. BMS-986183 dose expansion (Part 2) will include only subjects with HCC who have progressed or been refractory to at least 1 standard prior systemic treatment regimen (and not received more than 2 prior systemic treatments) AND with a plasma membrane or cytoplasmic H score \geq 50 for GPC-3 expression in the tumor tissue. The dose chosen for BMS-986183 dose escalation (Part 1). BMS-986183 and nivolumab dose expansion (Part 4) will include subjects who have received no prior systemic therapy for HCC AND with a plasma membrane or cytoplasmic H score \geq 50 for GPC-3 expression in the tumor tissue. The dose chosen for BMS-986183 dose escalation (Part 1). BMS-986183 and nivolumab dose expansion (Part 4) will include subjects who have received no prior systemic therapy for HCC AND with a plasma membrane or cytoplasmic H score \geq 50 for GPC-3 expression in the tumor tissue. The dose chosen for BMS-986183 and nivolumab dose escalation (Part 1). BMS-986183 and nivolumab dose expansion (Part 4) will include subjects who have received no prior systemic therapy for HCC AND with a plasma membrane or cytoplasmic H score \geq 50 for GPC-3 expression in the tumor tissue. The dose chosen for BMS-986183 and nivolumab dose expansion (Part 4) will be based on results (safety, PK, and all available data) from BMS-986183 and nivolumab dose expansion (Part 4) will be based on results (safety, PK, and all available data) from BMS-986183 and nivolumab dose escalation (Part 3).

All subjects will complete up to 4 study periods: screening (up to 28 days), treatment (for approximately 1 year or 17 cycles, with 21 days/cycle), safety follow-up (for a total of 60 days after the last dose of study drug for BMS-986183 dose escalation [Part 1] and BMS-986183 dose expansion [Part 2] and for a total of 100 days after the last dose of study drug for BMS-986183 and nivolumab dose escalation [Part 3] and BMS-986183 and nivolumab dose expansion [Part 4]), with simultaneous response and survival follow-up periods. All subjects will continue to be followed up to 6 months from last dose of study drug. Subjects in BMS-986183 and nivolumab dose escalation (Part 3) and BMS-986183 and nivolumab dose expansion (Part 4) may also be eligible for retreatment with their originally assigned dose regimen with disease progression during follow-up. Subjects in BMS-986183 dose expansion (Part 2) only who have disease progression may be eligible for a combination therapy extension option (see Section 3.1.2.1).

See Figure 3.1-1 and Figure 3.1-2 for a schematic of the study design and study periods, respectively.

Figure 3.1-1:Study Design

1L =first-line; 2L = second-line; Ref = refractory; Rel = relapse.

- ^a DLT Assessment Period is only for BMS-986183 dose escalation (Part 1) and BMS-986183 and nivolumab dose escalation (Part 3).
- ^b Response follow-up is simultaneous with survival follow-up. Only subjects with SD, PR, or CR will be followed for response at least every 3 to 4 months until progression, death, or initiation of new treatment (whichever occurs first).

C = Cycle 1 D = Day.

A total of approximately 151 subjects will be treated in the entire study, with approximately up to 30 subjects in BMS-986183 dose escalation (Part 1), approximately 50 subjects in BMS-986183

Revised Protocol No.: 03 Date: 03-May-2017 dose expansion (Part 2), approximately 21 subjects in BMS-986183 and nivolumab dose escalation (Part 3), and approximately 50 subjects in BMS-986183 and nivolumab dose expansion (Part 4). The approximate duration of the study is 4 years from the time of the first visit of the first subject to when the last subject has been followed for at least 6 months from his/her last date of treatment.

Screening Period:

The screening period will last for up to 28 days. Screening period begins after establishing the subject's initial eligibility and the subject's signing of the ICF. Specimens from tumor tissue must be provided (see Section 3.3.1 for details). The screening period either ends with confirmation of full eligibility and treatment assignment of the subject or with the confirmation that the subject is a screen failure. For information on re-screening, see Section 4.4. For details on re-enrollment, see Section 3.3.1.

Treatment Period:

Each treatment cycle consists of an IV infusion of BMS-986183 monotherapy (BMS-986183 dose escalation [Part 1] and BMS-986183 dose expansion [Part 2]) or BMS-986183 and nivolumab (BMS-986183 and nivolumab dose escalation [Part 3] and BMS-986183 and nivolumab dose expansion [Part 4]) once every 21 days. BMS-986183 monotherapy or BMS-986183 and nivolumab combination therapy will be given on Day 1 of each treatment cycle. The study drug is administered for approximately 1 year (17 cycles, with 21 days/cycle) or until complete remission, progression, unacceptable toxicity, withdrawal of consent, or study closure, whichever occurs first. Study assessments are to be collected as outlined in Table 5.1-1 and Table 5.1-2. Specific requirements for subjects treated with BMS-986183, including dose modifications, dose delays, and treatment discontinuation criteria are described in Section 4.5.2, Section 4.5.4, and Section 3.5, respectively. The treatment period ends when the subject is discontinued from study drug (see Section 3.5). Subjects will then enter the safety follow-up period.

Subjects with a response of SD, PR, or complete response (CR) at the end of a given cycle will continue to the next treatment cycle. Subjects with a confirmed CR at the end of the next cycle will discontinue treatment. Subjects will generally be allowed to continue study therapy for approximately 1 year (17 cycles, with 21 days/cycle) or until the subject meets criteria for discontinuation of study therapy as outlined in Section 3.5, whichever comes first.

Individual subjects with SD or PR may have 6 months (9 cycles, with 21 days/cycle) of extended treatment with BMS-986183 after the first treatment period (17 cycles, with 21 days/cycle) on a case-by-case basis after specific consultation and agreement between the investigator and BMS medical monitor.

Follow-up Period:

Safety Follow-up Period

All subjects will enter the safety follow-up period once the decision is made to discontinue the subject from treatment (eg, at end of treatment [EOT]).

After the EOT visit, all subjects will be evaluated for any new AEs for a total of 60 days after the last dose of study drug for BMS-986183 dose escalation (Part 1) and BMS-986183 dose expansion (Part 2) and for a total of 100 days after the last dose of study drug for BMS-986183 and nivolumab dose escalation (Part 3) and BMS-986183 and nivolumab dose expansion (Part 4). Follow-up visits should occur at 30 and 60 days (\pm 5 days) after the last dose. Subjects in BMS-986183 and nivolumab dose escalation (Part 3) and BMS-986183 and nivolumab dose expansion (Part 4) will have an additional visit at 100 days (\pm 10 days) after the last dose. All subjects will be required to complete their clinical safety follow-up visits regardless of whether they start new anti-cancer therapy, except those subjects who withdraw consent for study participation.

Subjects who develop toxicity requiring discontinuation of treatment will enter the safety follow-up period. The subject should be seen at least every 30 days, until the AE has resolved to baseline, stabilized, or been deemed irreversible.

Survival Follow-up Period

After completion of the safety follow-up period, all subjects will enter the survival follow-up period. All subjects will be followed by telephone contact, office visit, or documented clinic visit every 12 weeks (\pm 2 weeks) from his/her last dose of study drug for 6 months until progression or death. Both response and survival follow-up periods will occur simultaneously during the 6-month follow-up period. The duration of this period is up to 6 months following the subject's last dose of study drug. Subjects in the survival follow-up period who progress will be eligible to receive anti-cancer therapy as appropriate.

Retreatment during Survival Follow-up (Parts 3 and 4 only)

Retreatment may be allowed in BMS-986183 and nivolumab dose escalation (Part 3) and BMS-986183 and nivolumab dose expansion (Part 4) of this study for subjects with disease progression during follow-up. Subjects who complete approximately 1 year (17 cycles, with 21 days/cycle) of study therapy and who enter survival follow-up with ongoing disease control (CR, PR, or SD) for reasons other than drug-related toxicity may be eligible for retreatment, upon subsequent confirmed disease progression within 12 months of the last dose of study drug (on a case-by-case basis) after careful evaluation and discussion with the BMS Medical Monitor to determine whether the benefit/risk ratio supports administration of further study therapy. Subjects meeting criteria for retreatment will be treated up to approximately 1 year (17 cycles, with 21 days/cycle) with the originally assigned dose regimen (eg, same dose and dose schedule administered during the first approximately 1 year [17 cycles, with 21 days/cycle]) or modified dose regimen, unless that dose and schedule were subsequently found to exceed the MTD, in which case the subject will be treated at the next lower or alternate dose and schedule. Subjects entering this phase will follow the schedule as outlined in Table 5.1-3. Samples for PK will be collected less frequently (Table 5.5.1-3).

Response Follow-up Period

Subjects with SD, PR, or CR at study drug discontinuation will continue to have radiologic and clinical tumor assessments at least every 3 to 4 months during the survival follow-up period (Section 3.1) until progression, death, or initiation of new treatment (whichever occurs first).

Radiological tumor assessments for subjects who have ongoing clinical benefit may continue to be collected after subjects complete the survival follow-up period of the study. Subjects who have disease progression following treatment with study drug will not be evaluated for response beyond the EOT visit and will be allowed to receive other tumor-directed therapy as required.

3.1.1 Dose Escalation (BMS-986183 Dose Escalation [Part 1] and BMS-986183 and Nivolumab Dose Escalation [Part 3])

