3.6 Post Study Drug Follow-up

In this study, assessing the safety and tolerability of BMS-986183 in subjects with HCC is a key endpoint of the study. Post study follow-up is of critical importance and is essential to preserving subject safety and the integrity of the study. Subjects who discontinue study drug must continue to be followed for collection of outcome and/or survival follow-up data as required and in line with Section 5 until death or the conclusion of the study.

BMS may request that survival data be collected on all treated/randomized subjects outside of the protocol defined window (Table 5.1-2). At the time of this request, each subject will be contacted to determine their survival status unless the subject has withdrawn consent for all contacts or is lost to follow-up.

Safety follow-up Visit 1 will should occur 30 days from the last dose (\pm 5 days) or coinciding with the date of discontinuation of study drug (\pm 5 days). Safety follow-up Visit 2 will occur 60 days from the last dose (\pm 5 days). For BMS-986183 and nivolumab dose escalation (Part 3) and BMS-986183 and nivolumab dose expansion (Part 4) only, safety follow-up Visit 3 will occur 100 days from the last dose (\pm 10 days). Survival follow-up visits for all subjects will occur approximately every 12 weeks from their last follow-up visit. Survival follow-up visits may be performed by telephone contact, office visit, or documented clinic visit. Response follow-up visits (only for subjects with SD, PR, or CR) occur at least every 3 to 4 months during the survival follow-up period until progression, death, or initiation of new treatment (whichever occurs first).

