Nivolumab Administration	x			X					X					For BMS-986183 and nivolumab dose escalation (Part 3) and BMS-986183 and nivolumab dose

Procedure ^a	C2	2 and	C3		C4					ЕОТ	Follow- up (30 and 60 Days After Last Dose)	Follow- up (100 Days After Last Dose) ^c	Survival Follow-up ^d	Notes
	D1	D8	D15	D1	D2	D4 ^e	D8	D15	D1		(± 5 days)	(± 10 days)	(± 2 weeks)	
														expansion (Part 4) only. BMS-986183 is infused first followed by nivolumab. See Section 4 for administration details. See Section 3.1.1.2 for observation times. The start and stop time of the study drug infusion should be documented (start of drug infusion = 0 hour).
Other														
Other Anti-cancer Therapies													x ^j	
Subject Status													X	Also see tumor assessment schedule above

^a In the event that multiple procedures are required at a single timepoint, the ECG may be obtained up to 15 minutes earlier, vital signs may be obtained up to 10 minutes earlier or later, and clinical laboratory sample may be obtained up to 5 minutes earlier than the nominal PK timepoint, ensuring the PK samples can be collected on time.

^b Individual subjects with SD or PR may have 6 months (9 cycles, with 21 days/cycle) of extended treatment with BMS-986183 after the first treatment period (17 cycles, with 21 days/cycle) on a case-by-case basis after specific consultation and agreement between the investigator and BMS medical monitor. These subjects, as well as any subjects in BMS-986183 and nivolumab dose escalation (Part 3) or BMS-986183 and nivolumab dose expansion (Part 4) who meet the criteria to continue combination therapy beyond progression (see Section 4.5.7), will follow the assessment/procedure schedule for C5 to C17 subjects.

^c BMS-986183 and nivolumab dose escalation (Part 3) and BMS-986183 and nivolumab dose expansion (Part 4) only.

^d For all subjects, subject status will be assessed by telephone contact, office visit, or documented clinic visit every 12 weeks (± 2 weeks) up to 6 months from his or her last dose of study drug.

^e C4D4: ± 1 day.

f

Vital signs will be obtained before the BMS-986183 infusion and then every 30 minutes (\pm 10 minutes) until 30 minutes following completion of the last infusion. If any vital sign is abnormal at the final check, the subject must be observed further for a period of time, as clinically indicated. The start and stop time of the study drug infusion should be documented (start of drug infusion = 0 hour).

^g Only anti-cancer treatments.

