8.4.2 Efficacy Analyses

Efficacy results will be presented by dose and regimen. Individual BOR, DoR, and PFS will be listed using RECIST v1.1 criteria (Appendix 6).⁸¹ BOR outcomes will be tabulated by dose and dose regimen. The ORR and PFS rates (eg, at 24 weeks) and the CI will be provided by dose and dose regimen if there is enough data. The DoR and PFS will be estimated by K-M methodology, PFS rates (eg, at 24 weeks) will be similarly estimated, based on K-M methodology. Individual changes in the tumor burden over time will be presented graphically by dose. OS may also be assessed as part of exploratory efficacy analysis, by K-M plots and medians and OS rates at specified times, and by tabulation, graphics, and/or medians as appropriate for the endpoints.

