7.5.1 Deaths

Summary:

Deaths will be summarized by treatment:

- All deaths, reasons for death
- Deaths within 60 days of last dose received, reasons for death
- Deaths within 100 days of last dose received, reasons for death

Listing:

All recorded deaths for All Enrolled subjects will be listed by subject.

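### Protocol 3.1 stops survival contact at progression, while the schedule tables and 3.6 do not; if sites apply the 3.1 wording, deaths after the safety window may be missed and exploratory OS biased upward

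*Protocol*

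**What the plan says.** The Survival Follow-up Period paragraph of protocol 3.1 has every subject contacted every 12 weeks "from his/her last dose of study drug for 6 months until progression or death". Two sentences later it states: "The duration of this period is up to 6 months following the subject's last dose of study drug". It then adds: "Subjects in the survival follow-up period who progress will be eligible to receive anti-cancer therapy as appropriate". That last sentence treats a progressed subject as still in the period.

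The overview in 3.1 follows all subjects for up to 6 months from last dose. Table 5.1-2 footnote d says "For all subjects, subject status will be assessed by telephone contact, office visit, or documented clinic visit every 12 weeks", up to 6 months from last dose, with no stop at progression. Footnote j has survival and later therapies recorded while progressed subjects are in this period. Footnotes d and i of Table 5.1-3 match.

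Section 3.6 follows subjects "as required and in line with Section 5 until death or the conclusion of the study" and sets a different clock: "Survival follow-up visits for all subjects will occur approximately every 12 weeks from their last follow-up visit".

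On use of the data, protocol 8.4.2 says "OS may also be assessed as part of exploratory efficacy analysis", by Kaplan-Meier. SAP 7.1 also names Kaplan-Meier for overall survival. SAP 7.5.1 tabulates "All deaths, reasons for death", and separately deaths within 60 and within 100 days of last dose.

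**The concern.** Progression is a reason to stop study drug (protocol 3.5 and 4.5.6). A subject who stops for that reason has already met the 3.1 stop rule when survival follow-up begins. Read literally, only the safety visits to day 60 (Parts 1 and 2) or day 100 (Parts 3 and 4) remain.

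Censoring OS at that point is informative, because subjects leave the risk set just as their risk of death is likely to rise. Kaplan-Meier OS would then be biased upward and the all-deaths row would be an undercount. Sites following different sections would also contribute different lengths of follow-up to the same estimate.

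**Working it through.** **1. The rules side by side**

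| Place | Survival contact ends at | 12-week clock | Progressed subjects |
|---|---|---|---|
| 3.1, contact sentence | progression or death, within 6 months | from last dose | out |
| 3.1, same paragraph, later sentences | 6 months from last dose | not stated | in |
| 3.1, overview of periods | 6 months from last dose | not stated | in (all subjects) |
| Table 5.1-2, footnotes d and j | 6 months from last dose | no origin other than last dose | in |
| Table 5.1-3, footnotes d and i | 6 months from last dose | no origin other than last dose | in |
| 3.6 | death or study conclusion, in line with Section 5 | from last follow-up visit | in (all subjects) |

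Progression as a stop otherwise belongs to response follow-up, that is, the scans (3.1, 3.6, Table 5.1-2 footnote i). The phrase in the contact sentence looks carried over from there.

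**2. The clocks**

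Six months is 6 × 30.4375 = 182.6 days, using the SAP section 8 conversion.
- From last dose: contacts at days 84 and 168.
- Under 3.6, Parts 1 and 2: 60 + 84 = day 144, then day 228, beyond 6 months.
- Under 3.6, Parts 3 and 4: 100 + 84 = day 184, already at the 6-month limit, then day 268.

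**3. Deaths at risk of being missed**

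The plan gives no OS median, event count or hazard, so there is no figure to reproduce. I assume last dose at progression and exponential survival after progression with median m months, so F(d) = 1 − exp(−ln 2 × (d/30.4375)/m). The share of deaths within 6 months that fall after a safety window of w days is [F(182.6) − F(w)] / F(182.6).

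| m (months) | F(60) | F(100) | F(182.6) | Share after day 60 | Share after day 100 |
|---|---|---|---|---|---|
| 3 | 0.366 | 0.532 | 0.750 | 51% | 29% |
| 6 | 0.204 | 0.316 | 0.500 | 59% | 37% |
| 9 | 0.141 | 0.224 | 0.370 | 62% | 40% |
| 12 | 0.108 | 0.173 | 0.293 | 63% | 41% |

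For m = 3 and w = 60: (0.750 − 0.366)/0.750 = 0.512.

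**4. Effect on Kaplan-Meier OS**

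Simulation of 200,000 subjects per scenario:
- median time to progression or death 2, 4 or 6 months;
- 15% of first events are deaths without progression;
- median survival after progression 3, 6, 9 or 12 months;
- dosing stops at progression or day 357 (17 × 21).

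This gives 12 scenarios. The table shows 12-month OS in percent, with the excess over the true value in points, for five scenarios that include the extremes.

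| Median PFS / post-progression (months) | True | 6-month rule | 3.1 wording, 60-day window | 3.1 wording, 100-day window |
|---|---|---|---|---|
| 2 / 12 | 51.0 | 51.3 (+0.3) | 52.4 (+1.4) | 51.8 (+0.8) |
| 4 / 3 | 28.5 | 31.4 (+2.9) | 45.0 (+16.5) | 37.8 (+9.3) |
| 4 / 6 | 44.5 | 47.3 (+2.8) | 57.9 (+13.4) | 52.7 (+8.2) |
| 6 / 3 | 40.9 | 43.8 (+2.9) | 57.3 (+16.4) | 50.3 (+9.4) |
| 6 / 6 | 54.5 | 57.6 (+3.1) | 68.0 (+13.5) | 63.1 (+8.6) |

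Across all 12 scenarios the excess is 1.4 to 16.5 points (60-day), 0.8 to 9.4 (100-day) and 0.3 to 3.1 (6-month rule). Deaths recorded are 20 to 46% of subjects (60-day) and 25 to 60% (100-day), against 34 to 78% under the 6-month rule.

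At 6 months from first dose, the 6-month rule reproduces true OS in all 12 scenarios. This is expected: last dose cannot precede first dose, so every subject is followed at least that long.

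**The case against.** The strongest reply is that the documents already settle the reading. The paragraph containing the phrase keeps progressed subjects in the period, and so do the overview and the schedule footnotes. Section 3.6 defers to Section 5, which sets 6 months, and it lets the sponsor request survival status outside that window. This stands in part: the phrase is probably a slip and many sites would work from the table. But it is a stated rule in the design section, the sponsor's request is optional, and 3.6 still has its own clock.

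A reader might infer more than the documents support:

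- **That most later deaths go unrecorded and OS is overstated.** This requires sites to apply the 3.1 sentence and the analysis to censor accordingly. Within 6 months, the share at risk exceeds half only with the 60-day window; in Parts 3 and 4 it is 29 to 41%. The 6-month rule itself leaves later deaths uncaptured.
- **That the primary safety endpoint is compromised.** SAP 4.1 evaluates safety to 60 or 100 days after last dose. Safety visits in that window are required even if new therapy starts. Only the all-deaths row can vary.
- **That progression always ends dosing.** Protocol 4.5.7 (treatment beyond progression), 3.1.2.1 (the Part 2 combination extension) and 3.1 (retreatment) provide exceptions in Parts 2 to 4, about 50 + 21 + 50 = 121 of 151 subjects. The simulation does not model them.
- **That the SAP lacks an OS censoring rule.** None appears in the published text, but parts of that text have been removed, so its absence shows nothing.

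**Conclusion.** The contradiction is certain: the 3.1 contact sentence disagrees with its own paragraph, the overview and both schedule tables on whether survival status is collected after progression, and 3.6 adds a different end point and clock.

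The consequence is conditional and limited. If the 3.1 sentence is applied, the direction is an upward bias in exploratory OS and an undercount of all deaths. The ranges of about 1 to 17 points (60-day window) and 1 to 9 points (100-day window) at 12 months, against 0 to 3 under the 6-month rule, rest wholly on assumed exponential hazards, last dose at progression and literal application by every site. ORR, PFS and deaths within the safety window do not depend on this rule. The correction is worth making because it is nearly free.

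**What to change.** 1. In protocol 3.1, remove progression from the stop rule, so that status contact continues whether or not the subject has progressed.
2. Use one clock (from last dose) and one end point (the 6 months from last dose already in Table 5.1-2) in 3.1, 3.6 and the footnotes to Tables 5.1-2 and 5.1-3.
3. Report OS rates only over the horizon for which all subjects are followed. Under the 6-month rule that is 6 months from first dose, apart from loss to follow-up.

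The cost is protocol wording plus telephone contacts that Table 5.1-2 already schedules. Following everyone to death or study end would support later OS rates, but it is an optional and larger change: in a study of about 4 years with 12-weekly contacts, an early enrollee could need more than ten calls.
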